## 8.1.2.1.3 Dose Escalation Levels

The provisional doses to be administered during dose escalation are listed in Table 8-1.

Table 8-1 Provisional Dose Levels

Dose Level	Proposed VX-984 Dose (mg) a	Proposed PLD Dose (mg/m²) a
-1 b	120	30
1 (Starting Dose)	120	40
2	240	40
3	480	40
4	720	40

Proposed dose levels assume 100% escalation will be possible initially followed by up to 50% escalation. Doses beyond these levels are expected to be dictated by the BLRM.

## 8.1.2.1.4 Treatment Duration and Disease Assessments

At all dose levels of VX-984, subjects will complete a total of up to six 28-day cycles of VX-984 and PLD combination therapy. Subjects with tumors responding to treatment may continue treatment past 6 cycles with the agreement of the Investigator and medical monitor until disease progression, unacceptable toxicity, withdrawal of consent, or until exposure to PLD exceeds 550 mg/m^2. Staging CT scans will be performed at the end of every 2 cycles (see Table 3-3). If there is evidence of progressive disease as determined using RECIST 1.1, the subject's treatment will be discontinued. In addition, transthoracic echocardiograms will be performed at baseline and at the end of every 2 cycles (see Table 3-3). After 6 cycles, CT scans will be performed at the end of every 2 to 3 cycles (see Table 3-3).

## 8.1.2.1.5 Determination of MTD

Definition of MTD: The MTD is defined as the highest dose combination for a given schedule that causes DLTs in no more than 33.3% of subjects during the first cycle of treatment.

Dose escalation will continue until the identification of MTD or a suitable lower dose for Part B. This will occur when the following conditions are met:

- 1. at least 6 subjects have been treated at this dose
- 2. the dose satisfies one of the following conditions:
  - a. the posterior probability of targeted toxicity at this dose exceeds 50% and is the highest among potential doses, or
  - b. at least 15 subjects have been treated

The DLT Evaluable Set will be used for the determination of the MTD.

b. Dose level -1 represents a dose that may be evaluated if dose level 1 (starting doses of VX-984 and PLD) is poorly tolerated.

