#### **Data Analyses:**

Analysis of all data will be performed by the sponsor or designee. The demographics and baseline characteristics will be summarized by dose group, by concurrent regimen and study part, and overall. Baseline characteristics will include but will not be limited to the following variables: type of cancer, tumor stage at baseline, World Health Organization (WHO) performance status at baseline, time elapsed since cancer diagnosis, prior chemotherapy and radiation therapy, and duration of most recent cancer therapy.

The overall safety profile of VX-984 will be assessed in terms of the following primary safety endpoints:

- Incidence of treatment-emergent AEs (TEAEs), including AEs leading to dose modifications or discontinuations
- Incidence of DLTs (Part A)
- Clinical laboratory values
- ECG outcomes
- Echocardiogram outcomes
- Vital signs.

Safety data will be summarized by dose group, by concurrent regimen and study part, and overall. In general, safety analyses will be based on the Safety Set defined as all subjects who have received any study drug.

The summary of DLTs will be based on the DLT Evaluable Set. The BLRM will be used to estimate the posterior distributions for the probabilities of DLT events at various combination dose levels after each cohort of subjects. The MTD is defined as the combination dose associated with the highest probability that DLT events will occur in 16.6% to less than 33.3% subjects and as the combination dose that will not exceed the overdose criterion (<25% probability that DLT events will occur in  $\ge 33\%$  of subjects).

Efficacy data will be summarized by dose group, by concurrent regimen and study part, and overall. For Part B, the proportion of subjects demonstrating ORR, together with exact 90% CI, will be presented.

VX-984 PK data will be analyzed on an ongoing basis during dose escalation in Parts A and B using standard noncompartmental methods. PK data for VX-984 will be reviewed with safety data to inform dose escalation.

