#### 12.3.3 Determination of the MTD

The determination of the MTD is based on an adaptive BLRM guided by the EWOC principle using the methodology described in detail in Section 12.3.3.2. The MTD will be further evaluated for anti-tumor activity and overall tolerability during the dose expansion phase of the trial.

After the dose expansion phase (Part B), the final recommended dose for future development will be based on considerations of the MTD estimated by the BLRM, and on an overall clinical assessment of all available safety, tolerability, PK, and PD data from all cycles at all different dose levels tested, in both phases of the study. If it is determined that treatment at a dose of VX-984 in combination with PLD lower than the MTD established during the dose escalation of the study is better tolerated, and has a better PK/PD or efficacy profile based on clinical considerations, then that dose may be used in further development.

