#### 12.3.3.1 MTD

The MTD is defined as the highest dose combination for a given schedule that causes DLTs in no more than 33.3% of subjects during the first cycle of treatment. Estimation of the MTD during the dose escalation phase of the study will be based upon the posterior distribution of the incidence of DLT in Cycle 1 in subjects in the DLT Evaluable Set. The corresponding methodology is described in Section 12.3.3.2. The variable of interest for the determination of MTD is the frequency of DLTs associated with the administration of VX-984 in combination with PLD during the first cycle of treatment.

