### 12.3.3.2 Statistical Model and Method of Analysis

An adaptive BLRM with  $\geq 2$  parameters, guided by the EWOC principle, will be used to make dose recommendations and estimate the MTD during the escalation phase of the study, with the following 2 exceptions:

• For cohorts requiring 3 or more evaluable subjects, if only 2 evaluable subjects are available for assessment (all others drop out), and neither subject has had a

treatment-related or possibly-related toxicity greater than CTCAE Grade 1, then 2 subjects will be considered sufficient for decision-making

• If the first 2 subjects in a cohort have DLTs, no additional subjects will be enrolled into that cohort until the Bayesian model has been updated with this new information. Likewise, the model will be re-evaluated if 2 subjects in a cohort have DLTs before the enrollment of any additional subjects.

The DLT relationship in the escalation part of the study will be described by the following BLRM:

$$logit\{\pi(d_j, x_1, ..., x_k)\} = \log(\alpha) + \beta \log\left(\frac{d_j}{d^*}\right) + \sum_{i=1}^k \gamma_i x_i$$

Under-dosing:  $\pi(d) \in [0.00, 0.166)$ 

Target toxicity:  $\pi(d) \in [0.166, 0.333)$ 

Excessive toxicity:  $\pi(d) \in [0.333, 1.00]$ 

where  $logit(\pi) = ln(\pi/(1 - \pi))$ , where  $\pi$  is the probability of a DLT.

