#### 12.3.3.3 Dose Recommendation

#### Part A

After each cohort of subjects the posterior distribution for the model parameters will be obtained through Gibbs' sampling procedures by updating the prior distribution with the most up-to-date DLT information. Based on the posterior distribution of all model parameters, the corresponding posterior distributions for the probabilities of DLT at different dose levels are obtained. The results of this analysis are summarized in terms of the estimated probabilities that the true rate of DLT at each dose level will have of lying in each of the following intervals:

• [0, 0.166) under-dosing • [0.166, 0.333) targeted toxicity • [0.333, 1.00] excessive toxicity

Following the principle of EWOC, after each cohort of subjects the recommended dose is the one with the highest posterior probability of the DLT rate falling in the target interval [16.6%, 33.3%) among the doses fulfilling EWOC, i.e., it is unlikely (< 25% posterior probability) that the DLT rate at the dose falls in the excessive toxicity interval.

Note that the dose that maximizes the posterior probability of targeted toxicity is the best estimate of the MTD, but it may not be an admissible dose according to the overdose criterion if the amount of data is insufficient. If vague prior information is used for the

probabilities of DLT in the early stages of the study, this escalation procedure will reflect a conservative strategy.

The dose recommended by the adaptive BLRM may be regarded as guidance and information to be integrated with a clinical assessment of the toxicity profiles observed at the time of the analysis in determining the next dose level to be investigated.

The final recommended dose will be based on considerations of the MTDs estimated by the BLRM and on an overall clinical assessment of all available safety, tolerability, PK, and PD data from all cycles at all different dose levels tested.

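### Protocol 8.1.2.1.5 lets the MTD be identified without the 25% overdose limit that the synopsis makes part of the MTD definition

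*Protocol*

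**What the plan says.** The protocol describes the MTD in several places.

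- **Synopsis, Data Analyses.** The MTD is the dose with the highest probability of a DLT rate from 16.6% to below 33.3%. It must also be "the combination dose that will not exceed the overdose criterion", which is given there as less than 25% probability of a DLT rate of 33% or more.
- **Section 8.1.2.1.5.** The MTD is the highest combination with DLTs in no more than 33.3% of subjects in the first cycle. Escalation runs until the MTD, or a suitable lower dose for Part B, is identified. This requires at least 6 subjects at the dose, and that "the dose satisfies one of the following conditions". Condition 2a is that "the posterior probability of targeted toxicity at this dose exceeds 50% and is the highest among potential doses". Condition 2b is that "at least 15 subjects have been treated".
- **Section 12.3.3.** "The determination of the MTD is based on an adaptive BLRM guided by the EWOC principle". Section 12.3.3.1 adds that estimation of the MTD "will be based upon the posterior distribution of the incidence of DLT in Cycle 1". Section 12.3.3.2 says that the model, "guided by the EWOC principle, will be used to make dose recommendations and estimate the MTD".
- **Section 12.3.3.3, Part A.** The 25% limit governs the dose recommended after each cohort. The dose with the highest target probability is called the best estimate of the MTD, with the caution that "it may not be an admissible dose according to the overdose criterion if the amount of data is insufficient".
- **SAP 15.1.** It repeats the 33.3% definition, has no overdose term, and plans a table of subjects with and without DLTs.

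**The concern.** Section 8.1.2.1.5 is where a team would look to decide whether the MTD has been reached, and its list omits the overdose limit. The numeric limit in 8.1.2.1.2 and 12.3.3.3 applies to the next cohort's dose. That check is made before the cohort is treated; the MTD is declared after its DLTs are known. A dose can pass the first and fail the second.

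Section 8.1.2.1.2 makes the gap visible. After 2 DLTs in a new cohort at a previously tested dose, more subjects may be added there only if the dose still meets the overdose criteria. A dose closed to enrolment on that ground could still satisfy 8.1.2.1.5.

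The MTD is a primary endpoint of Part A. On the same data, the synopsis could reject a dose that 8.1.2.1.5 accepts. SAP section 7 drops Part B, so what is at stake is the reported MTD, not the dosing of an expansion cohort.

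**Working it through.** **1. What the conditions imply.** This step needs no prior. Write U, T and E for the posterior probabilities of the under-dosing, target and excessive intervals, so U + T + E = 1.

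- Condition 2a requires T > 0.50. Then E = 1 − T − U < 0.50 − U, so E can lie anywhere below 0.50.
- The synopsis requires E < 0.25, that is T + U > 0.75. Condition 2a does not imply this.
- Condition 2b contains no posterior probability, so it sets no bound on E.

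**2. Can the conflict arise when every BLRM assignment obeys the limit?** The protocol gives no numerical prior, so these are assumptions: the protocol's logistic model with reference dose 720 mg and no covariates; log(β) ~ N(0, 1); log(α) normal, centred on a DLT rate at 720 mg of 10%, 15% or 25% (SD 2) or 33% (SD 1.5). Each dose after the first DLT has the highest T among doses with E < 0.25, and is lower after 2 DLTs at an untested dose.

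*Path 1, intermediate doses in 60 mg steps.* DLTs are 0/3 at 120 mg, 0/3 at 240 mg, 2/3 at 480 mg, 2/4 at the model's intermediate dose, then 2/4 at 240 mg. The total at 240 mg is 2/7 (28.6%), with 3 + 7 + 3 + 4 = 17 subjects in the trial.

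| Prior median at 720 mg | Intermediate dose | E at 240 mg when assigned | E at 240 mg after 2/7 | T at 240 mg after 2/7 |
|---|---|---|---|---|
| 10% | 360 mg | 0.143 | 0.304 | 0.552 |
| 15% | 360 mg | 0.148 | 0.313 | 0.546 |
| 25% | 300 mg | 0.205 | 0.374 | 0.524 |
| 33% | 360 mg | 0.158 | 0.324 | 0.543 |

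Under all four priors, 240 mg has the highest T, so 2a is met, while E fails the limit. A second calculation agreed to within 0.003. Under the 25% prior the intermediate dose is a near-tie: E at 360 mg is 0.2506. Using 360 mg there gives E = 0.329 and T about 0.54, the same conclusion.

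*Table 8-1 doses only.* With 0/3 at 120 and 240 mg, 4/13 (30.8%) at 480 mg and 2/3 at 720 mg, E at 480 mg is 0.28 to 0.32 and 2a is met under all four priors. This shows that the conflict does not need 60 mg steps. It is a data set, not a path traced cohort by cohort.

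*Data that do not conflict.* With 2/8 at 480 mg, the count used as an example in 8.1.2.1.2, and 2/3 at 720 mg on Table 8-1 doses, E is 0.18 to 0.22 and passes. It fails (0.254 to 0.329) only when a further 2/4 at 540 or 600 mg is added.

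**3. How often?** The simulation used the same four priors, three dose sets, four true DLT curves, cohorts of 3 or of 3 to 6, both readings of 2b, and 2,000 trials per setting. The dose just tested was declared once 8.1.2.1.5 was met. Since 1/3 = 33.33…% exceeds 33.3%, a literal reading excludes an observed one third.

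| Observed 1/3 | Declared MTDs failing the limit | Median |
|---|---|---|
| Excluded | 0% to 8% | 2% |
| Counted | 1% to 22% | 9% |

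Where one third counts, 41% to 100% of the failing declarations sit exactly there. The simulation was not recomputed as the posteriors in step 2 were, so it deserves less weight.

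**The case against.** The strongest reply is that the limit is already in force. The synopsis defines the MTD by it, and 12.3.3 and 12.3.3.2 say that determination and estimation of the MTD are guided by EWOC, which has one numeric meaning in this protocol. The Part B re-check (8.1.2.2 and 12.3.3.3) asks whether the MTD continues to meet the overdose criteria, which presumes that it did so at the start. On this view 8.1.2.1.5 only says when enough data exist to stop, and 8.1.2.1.8 also requires consensus among Investigators and sponsor. A reader might infer from 8.1.2.1.5 that the authors meant to waive overdose control at declaration; these sections rule that out. What remains is that 8.1.2.1.5 says identification occurs when its own conditions are met, and that neither the guiding statements nor the consensus step sets a limit at declaration.

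A reader might also take the caution in 12.3.3.3 as an admission that doses meeting 2a are inadmissible. It is narrower: it applies when data are insufficient.

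The objection on size largely stands. Path 1 depends on step size: its return to 240 mg holds under one of the four priors with 40 mg steps, and under none with 30 or 20 mg steps. The simulation declares automatically, without the clinical review that consensus would bring.

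**Conclusion.** The inconsistency is real and follows from the text alone: 8.1.2.1.5 can accept as MTD a dose that the synopsis rejects. Its severity is minor to moderate. The conflict is reachable under several assumed priors but infrequent, with a median of about 2% of declarations under the literal 33.3% reading and about 9% if an observed one third counts. These figures rest on assumed priors, dose steps and true DLT curves; the bound of just under 50% under 2a does not.

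It would be going too far to infer that subjects would be assigned overly toxic doses. The limit still governs the model's recommendation for each new cohort, and Part B is not being pursued. Nor do the documents support saying that the example of 2 DLTs in 8 subjects in 8.1.2.1.2 breaches the limit by itself.

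**What to change.** Add a third required condition to 8.1.2.1.5, common to 2a and 2b: at declaration, on all DLT-evaluable data, the posterior probability that the DLT rate at the dose is 0.333 or more is below 25%. Put the same criterion in SAP 15.1, with the posterior reported for the declared dose. A change to the protocol alone would leave the SAP's definition of the reported MTD as it is.

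As a secondary clarification, state in 2b whether the 15 subjects are at this dose or in the trial. The stem of condition 2 favours this dose, but condition 1 says so explicitly and 2b does not.

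The cost is a few lines of text, and an occasional declaration that needs another cohort or a lower dose. In the simulation, mean Part A size rose by at most 0.8 subjects (one third excluded) or 1.7 (counted), and trials ending without an MTD rose by at most about 3 percentage points. The gain is also limited. Declarations at a dose whose true DLT rate was 0.333 or more changed by between a rise of 0.5 points and a fall of 2.2 (excluded), or between a rise of 0.6 and a fall of 12.0 (counted). The main benefit is a single rule for the primary endpoint.

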# 8.1.2.1.6 Definition of Dose-Limiting Toxicity

DLTs will be identified throughout the dosing cycles. DLTs will be defined using the National Cancer Institute (NCI) CTCAE (Version 4.0).

**Table 8-2** Criteria for Defining Dose-Limiting Toxicities

Toxicity	Any of the Following Criteria
Hematology	Neutropenia Grade 4 for > 7 days duration a
	Febrile neutropenia (fever of unknown origin without clinically or microbiologically documented infection)
	Thrombocytopenia Grade 3:
	o associated with clinically significant bleeding
	o requiring platelet transfusion
	Thrombocytopenia Grade 4
Cardiac	• QTc prolongation (any QTc interval ≥ 500 msec or any change in QTc interval ≥ 60 msec from baseline) on ECG, unless related to an electrolyte abnormality and prolongation resolves with correction of electrolyte abnormality
	• Any of the following (CTCAE criteria): Grade 2 or greater ventricular arrhythmia (second or third degree AV block), severe sustained/symptomatic sinus bradycardia less than 45 beats per minute (bpm) or sinus tachycardia > 120 bpm not due to other causes (e.g., fever), persistent supraventricular arrhythmia (e.g., uncontrolled/new atrial fibrillation, flutter, atrioventricular nodal tachycardia, etc.) lasting more than 24 hours, ventricular tachycardia defined as > 9 beats in a row or any length of torsades de pointes (polymorphic ventricular tachycardia with long QTc), or unexplained recurrent syncope
	• Symptoms suggestive of congestive heart failure with confirmed ejection fraction (EF) < 40% (by 2D-echocardiogram or multiple gated acquisition [MUGA] scan) or a relative decrease > 20% from historical assessment of EF performed within 12 months
	Troponin T: level that is confirmed with myocardial infarction
Hepatic	Any Grade 4 elevation of AST or ALT of any duration
	Any Grade 3 elevation of AST or ALT lasting more than 7 days
	• Any Grade 3 elevation of AST or ALT concomitant with Grade 2 elevation of bilirubin (for subjects with normal baseline bilirubin) or Grade 3 elevation of bilirubin (for subjects with Grade 1 bilirubin abnormality at baseline)
	Any Grade 3 elevation in bilirubin
Dermatologic	• Grade 3 rash for > 7 consecutive days, despite skin toxicity treatment (as per local practice) or any Grade 4 rash

Toxicities resulting in treatment interruption	• Any drug-related toxicity that causes interruption of treatment for > 2 weeks (14 successive days)
Other adverse events	• Infection (documented clinically or microbiologically) with Grade 3 or 4 neutropenia (absolute neutrophil count < 1.0 × 10  /L)
	• Grade 3 or 4 toxicity to organs other than the bone marrow, including Grade 3 and 4 biochemical AEs
	Death due to drug-related complications
Exceptions to	Grade 3 nausea
DLT criteria	• Grade 3 vomiting in subjects who have not received optimal treatment with anti-emetics
	Grade 3 diarrhea in subjects who have not received optimal treatment with antidiarrheal
	• Any Grade 3 elevation of AST or ALT lasting ≤ 7 days b
	Any elevation of ALP
	Acute infusion-related reactions

In the event of a Grade 4 neutropenia, a complete blood count (CBC) must be performed no more than 7 days after the onset of the event to determine if a DLT has occurred. Continue to monitor the subject closely until resolution to Grade 3 or lower.

If any change is made to the grade or causality of an AE during the study that may alter its DLT status, the sponsor must be informed immediately because this may affect dose escalation decisions.

# 8.1.2.1.7 Subject Evaluability

All subjects who meet the eligibility criteria and receive at least 1 dose of VX-984 will be evaluable for safety.

In order for subjects to be evaluable for dose escalation decisions:

- Subject must receive PLD on Day 1 and receive all 3 doses of VX-984 within 5 days (Days 2 to 6) with the first dose of VX-984 on Day 2; or
- The subject must have had a DLT during Cycle 1.

Subjects who do not fulfill at least 1 of the 2 above criteria will not be evaluable for dose escalation decisions and will be replaced.

In the event of a Grade 3 or higher elevation in ALT or AST, follow-up laboratory assessments should be performed every 48 to 72 hours until reduced to Grade 2 or lower.

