- In the event of a DLT, an adaptive Bayesian logistic regression model (BLRM) will be used to determine the dose for the subsequent cohorts or determine if the current dose level should be expanded. The adaptive BLRM will be guided by the escalation overdose control (EWOC) principle to control the risk of DLT in future subjects as described in Section 12.3.3.2. At each predicted dose, 3 to 6 subjects will be enrolled in each cohort at the discretion of the sponsor and Investigators as described in Section 8.1.2.1.8. If more than 3 subjects are enrolled, the first 3 subjects will receive VX-984 in the Lead-in Period and if no DLT is observed with VX-984 dosing then the additional subjects in the cohort will not have the Lead-in Period. The Lead-in Period will be required only if the dose of VX-984 is escalated beyond the highest dose of VX-984 previously tolerated in a Lead-in Period
- If 2 subjects in a previously untested dose level experience a DLT, enrollment to that cohort will stop, the BLRM will be updated and the next cohort will be opened at a lower dose level or an intermediate dose level that satisfies the EWOC criteria. However, if 2 subjects in a new cohort at a previously tested dose level experience a DLT (e.g., a total of 8 subjects are tested on this dose level with 2 DLTs observed), further enrollment to that cohort will stop, the BLRM will be updated with this new information and re-evaluation of the available safety, PK and PD data will occur. By

incorporating information gained at the preceding dose levels, additional subjects may be enrolled into the current dose level only if the dose still meets the EWOC criteria and as agreed by the sponsor and Investigators.

A subject will be considered as evaluable for dose determination if they have a DLT during Cycle 1 or the preceding Lead-in Period, or meet the minimum treatment and safety evaluation requirements for the first cycle as outlined in Subject Evaluability.

After completion of Cycle 1 of each cohort (3 to 6 subjects), available safety, PK, and efficacy information as well as recommendations from the Bayesian model will be used to determine the dose for the next cohort, with the following 2 exceptions:

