- 1. For cohorts requiring 3 or more evaluable subjects, if only 2 evaluable subjects are available for assessment (all others drop out), and neither subject has had a treatment-related or possibly-related toxicity greater than CTCAE Grade 1, then 2 subjects will be considered sufficient for decision-making
- 2. If the first 2 subjects in a cohort have a DLT, further enrollment to the study will be temporarily suspended and the Bayesian model will be updated with this new information. If the Bayesian model supports enrolling the next cohort at the dose level where 2 DLTs occurred, or at a higher dose level, the relevant data and rationale will be discussed and agreed upon by sponsor and the Investigators of the escalation phase. If sponsor and the Investigators agree that it is medically appropriate to enroll an additional cohort at the dose level where 2 DLTs occurred or at a higher dose, the data and rationale supporting this decision will be documented.

Following the principle of escalation with overdose control (EWOC), after each cohort the recommended dose will be the one with the highest posterior probability of the DLT rate falling in the target toxicity interval [0.166, 0.333) among the doses fulfilling EWOC. Per EWOC, it should be unlikely (< 25% posterior probability) that the DLT rate at the dose will exceed 0.333.

For further understanding of the safety, tolerability, and PK of VX 984 in combination with PLD, additional cohorts of subjects may be enrolled at preceding dose levels, or to intermediate dose levels before or while proceeding with further dose escalation. The maximum planned dose of VX-984 is 2000 mg during escalation, however, higher doses up to 3000 mg may be allowed depending on the observed safety, PK, and PD, and based on recommendation of the BLRM.

After repeating the above steps, the dose escalation of VX-984 will continue with a constant dose of PLD at 40 mg/m^2 until MTD is achieved.

If a dose of VX-984 is not tolerated with PLD at 40 mg/m², then the VX-984 dose may be reduced by up to 50% with a constant dose of PLD at 40 mg/m² or the dose of PLD will be reduced by 25% (30 mg/m²) or lower with a constant dose of VX-984. These doses will be explored in subsequent cohorts at the discretion of the Investigators and sponsor. If daily dosing of VX-984 for 3 days after PLD is not tolerated during initial dose escalation, less frequent dosing of VX-984 may be explored in subsequent cohorts.

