### 9.6 Replacement of Subjects

In Part A, subjects who withdraw or are withdrawn from treatment for reasons other than DLT before the Cycle 1 Day 28 assessment and who have not had the minimum exposure to study drugs described in Subject Evaluability will be replaced. Subjects who withdraw or are withdrawn from treatment beyond Cycle 1 will not be replaced.

For Part B, subjects who discontinue for reasons other than disease progression or are non-evaluable for efficacy analysis may be replaced. Subjects who discontinue for disease progression before the completion of Cycle 1 may also be replaced.

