# 12.2 Analysis Sets

#### For Part A:

• The DLT Evaluable Set is defined as all subjects in the Safety Set of Part A who either meet the minimum exposure criterion and have sufficient safety evaluations (as determined by the Investigators and sponsor), or have had a DLT during Cycle 1 (including the Lead-in Period)

A subject is considered to have met the minimum exposure criterion at a dose level if the subject received PLD on Day 1 and 3 doses of VX 984 within 5 days with the first dose of VX-984 on Day 2. Subjects who do not have a DLT during Cycle 1 are considered to have sufficient safety evaluations if they have been observed through the end of Cycle 1 following the administration of PLD and VX-984, and are considered by both the sponsor and Investigators to have enough safety data to conclude that a DLT did not occur

- The Safety Set is defined as all subjects who received at least 1 dose of study drug. The Safety Set will be used for safety analyses
- The Full Analysis Set is defined as all subjects who received at least 1 cycle of study drug and have a baseline scan. The Full Analysis Set will be used for efficacy analyses.

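### A fully dosed, DLT-free subject lost to observation before Day 28 counts as evaluable for escalation and is not replaced, but is outside the set used for the BLRM and MTD

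*Protocol*

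**What the plan says.** **Evaluability for escalation.** Protocol 8.1.2.1.7 gives two routes. The first is exposure: "Subject must receive PLD on Day 1 and receive all 3 doses of VX-984 within 5 days (Days 2 to 6", with the first VX-984 dose on Day 2. The second is toxicity: "The subject must have had a DLT during Cycle 1". The section then says: "Subjects who do not fulfill at least 1 of the 2 above criteria will not be evaluable for dose escalation decisions and will be replaced". It sets no observation requirement.

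**Replacement.** Protocol 9.6 covers Part A subjects who leave treatment before the Cycle 1 Day 28 assessment for reasons other than DLT, "and who have not had the minimum exposure to study drugs described in Subject Evaluability will be replaced". Missing the exposure is part of the condition.

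**Cross-reference.** Protocol 8.1.2.1.2 describes evaluable subjects as those who have a DLT in Cycle 1 or the Lead-in Period, or who "meet the minimum treatment and safety evaluation requirements for the first cycle as outlined in Subject Evaluability". Subject Evaluability (8.1.2.1.7) contains the treatment requirement but no safety evaluation requirement.

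**DLT Evaluable Set.** Protocol 12.2 asks for exposure and adequate safety data together. Its standard for DLT-free subjects reads: "considered to have sufficient safety evaluations if they have been observed through the end of Cycle 1 following the administration of PLD and VX-984". The sponsor and Investigators must also agree that the data suffice to conclude that no DLT occurred. SAP 8.2 likewise requires observation through the end of Cycle 1. Protocol 8.1.2.1.5 and 12.3.3.1 base the MTD and its model estimate on this set.

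**Short cohorts.** Exception 1 in 8.1.2.1.2 accepts two subjects as sufficient "if only 2 evaluable subjects are available for assessment (all others drop out), and neither subject has had a" related or possibly related toxicity above CTCAE Grade 1.

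**The concern.** The protocol has two definitions of an evaluable subject. The looser one stands where sites and the dose-escalation meeting would look for it. A subject who took every Cycle 1 dose, had no DLT and was then lost to observation meets the looser definition and fails the stricter one.

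The first thing at stake is the cohort count. Before the first DLT, escalation is rule-based on three subjects, with steps of up to 100%, in a first-in-human trial. Counting the leaver as the third evaluable subject lets a cohort look complete when one subject's DLT window was only partly seen. It also arguably avoids the stricter toxicity condition that exception 1 sets when only two subjects remain. The second is consistency: the cohort decision and the MTD estimate can rest on different denominators.

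**Working it through.** **Step 1: apply each rule to one subject.** Take a Part A subject who receives PLD on Day 1 and VX-984 on Days 2, 3 and 4, has no DLT, and withdraws consent on Day 10. Under Protocol 9.5 no further evaluations follow withdrawal of consent.

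| Section | Test | Result |
|---|---|---|
| Protocol 8.1.2.1.7 | Exposure, or a Cycle 1 DLT | Exposure met: evaluable, not replaced |
| Protocol 9.6 | Left before Day 28 and exposure missed | Exposure not missed: not replaced |
| Protocol 12.2 | Exposure and observation through Cycle 1, or a DLT | Not observed: outside the set |
| SAP 8.2 | Same two conditions, or a DLT | Outside the set |
| Protocol 8.1.2.1.5, 12.3.3.1 | MTD uses the DLT Evaluable Set | Subject not used |

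The SAP's later sentence about subjects who do not satisfy either criterion is loosely worded. Its opening sentence joins the two criteria with *and*, so the exclusion stands.

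**Step 2: how much of the window can be missing.** The exposure rule is met on Day 4, or on Day 6 at the latest. A subject last seen on Day 6 leaves (28 − 6)/28 = 22/28 = 79% of the days unobserved. Share of days is not share of DLT risk, but some DLTs cannot be judged that early. Table 8-2 has criteria that need Grade 4 neutropenia, Grade 3 AST/ALT elevation or Grade 3 rash to last more than 7 days. After Day 1, Table 3-3 schedules hematology on Days 8 and 15.

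**Step 3: the two-subject condition.** Suppose one of the other two subjects has a related Grade 2 toxicity, there is no other toxicity, and no earlier subject had Grade 2. Under the 12.2 definition the cohort has two evaluable subjects and exception 1 is not met. Under 8.1.2.1.7 it has three, and a single Grade 2 toxicity does not block a step of up to 100%.

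**Step 4: illustrative size.** The plan gives no figure to reproduce. Let p be the true Cycle 1 DLT rate and f the share of the leaver's DLT risk that was observed. The documents do not give f, so it is an assumption and is shown over a range.

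- Three fully observed subjects: P(no DLT) = (1 − p)³
- One early leaver: P(no observed DLT) = (1 − p)² × (1 − f·p)

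For p = 0.333: 0.667³ = 0.297. With f = 0.5: 0.667² × (1 − 0.5 × 0.333) = 0.4449 × 0.8335 = 0.371.

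| True rate p | All three observed | f = 0.75 | f = 0.5 | f = 0.25 | f = 0 (limit) |
|---|---|---|---|---|---|
| 25% | 42.2% | 45.7% | 49.2% | 52.7% | 56.3% |
| 33.3% | 29.7% | 33.4% | 37.1% | 40.8% | 44.5% |
| 50% | 12.5% | 15.6% | 18.8% | 21.9% | 25.0% |

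**The case against.** Four arguments narrow the point.

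1. **Stopping drug is not losing observation.** A reader might infer that every fully dosed subject who leaves treatment goes unobserved. The documents do not support that. Protocol 9.5 keeps withdrawn subjects in follow-up unless they withdraw consent. Protocol 8.1.4 gives every subject a Safety Follow-up Visit 28 (± 7) days after the last dose, which for a last dose on Day 4 is Day 25 to Day 39. This stands: the gap is confined to withdrawal of consent or loss to follow-up.

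2. **Other sections call for 28 days of data.** Protocol 8.1.2.1.2 makes escalation from the starting dose depend on tolerance through one 28-day cycle and carries that approach forward. Section 8.1.2.1.8 has each subject's course discussed, reviews data up to Day 28 and requires consensus. A reader might infer that escalation on an unobserved subject would pass unnoticed. These provisions make that unlikely. They remain partial safeguards, because neither makes the leaver non-evaluable or has the leaver replaced.

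3. **Exception 1 may still apply.** It turns on who is available for assessment, and a subject lost on Day 10 has dropped out. It would be too strong to say that the stricter condition can never apply. The text supports both readings, which is itself a reason to settle it.

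4. **The limit of 44.5% is not reached.** A subject meeting the exposure rule has been dosed, with Cycle 1 visits scheduled on Days 1, 2, 4 and 5. Where there is a Lead-in, DLTs there count too under 12.2. No observed DLT is also not the same as clearance for a step of up to 100%, which further requires no Grade 3 or worse toxicity and no Grade 2 toxicity in two subjects.

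**Conclusion.** The contradiction holds, in a narrow form. Protocol 8.1.2.1.7 and 9.6 count a fully dosed, DLT-free subject as evaluable and do not replace that subject on exposure alone; Protocol 12.2 and SAP 8.2 exclude the same subject if observation ended before the end of Cycle 1. The cross-reference in 8.1.2.1.2 does not close the gap, because the requirement it points to is not there.

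At a true DLT rate of 33.3%, one such leaver raises the chance of no observed DLT in a cohort of three from 29.7% to about 33% to 41%. This assumes that 75% to 25% of the leaver's DLT risk was observed, that subjects are independent, and that leaving is unrelated to DLT risk. The figures are conditional on a leaver occurring, and the documents give neither dropout frequency nor DLT timing.

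A reader might infer that the MTD estimate itself is compromised. It is not, on this point: it uses the stricter set and drops the leaver. That protects the estimate, but not the cohort decision already taken. The issue is safety-relevant, and the protocol already holds a definition that resolves it.

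**What to change.** Reconcile Protocol 8.1.2.1.2, 8.1.2.1.7, 9.6 and 12.2 on the definition already in 12.2.

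- **8.1.2.1.7:** require the stated exposure plus observation through the end of Cycle 1 with enough safety data to conclude that no DLT occurred; or a DLT during Cycle 1 including the Lead-in Period. The cross-reference in 8.1.2.1.2 then points to text that exists.
- **9.6:** base replacement on not meeting that evaluability definition, rather than on missed exposure. Do not tie it to membership of the DLT Evaluable Set, because SAP 8.2 removes replaced subjects from that set and the rule would be partly circular.
- **8.1.2.1.2, exception 1:** state how replacement and the exception fit together when only two such subjects remain.
- **SAP 8.2:** carry the same wording, including the Lead-in Period, which its definition of the set does not mention.

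The cost is a short protocol amendment, an occasional replacement subject and a short delay to a cohort decision. If escalation has already finished, the clinical study report should identify any subject who was counted in a cohort decision but is outside the DLT Evaluable Set. The listing of exclusions planned in SAP 10.2 supplies part of what is needed.
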